#### **4.4 Data Collection**

In conjunction with Ministry of Health and local collaborators we will undertake case searches for individuals with yaws and yaws-like lesions in selected communities. All study staff involved in the field surveys will be extensively trained in the clinical, diagnostic, and public health aspects of yaws. The initial screening will involve a quick examination to determine if people have yaws lesions present. All people with lesions and around 6000 people without any clinical evidence will then be invited into sub study 1. Those enrolled will provide demographic data and risk factor data (Appendix A and B). Those with yaws will undergo a more thorough skin examination to look for evidence of clinically active yaws and this will be recorded into a case report form (CRF) (see Appendix B) and may note the presence of other skin conditions. Yaws-like lesions will be assessed using WHO recommended procedure  (Appendix C), with a simplified system of WHO yaws pictorial guide used to define each yaws-like lesion. These will be marked on a diagram and lesions will be photographed for quality control purposes (Appendix B). Each participant will be assigned a unique study identification number and all data will be recorded and analysed with this unique identification number. Study data will be electronically entered into a Good Clinical Practice (GCP)-compliant, offline, trial-specific mobile application [Research Electronic Data Capture (REDCap), Nashville, TN, USA] or Open Data Kit (ODK).

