## 1.3 Study design:

This study will take place in three sub-Saharan African countries known to be endemic for yaws. We aim to screen approximately 60,000 participants, of all ages. Screened participants will undergo primary clinical examination for yaws-like lesions and will be classed as either suspected yaws or negative for active yaws. A proportion of the yaws free participants ( $\approx 10\%$ ) and all those with suspected yaws ( $\approx 6000$  people) will be invited to answer a questionnaire relating to household demographics and possible risk factors for yaws. If resources allow they will also be asked to provide dried blood spots for future serological analysis of yaws and other co-endemic neglected tropical diseases. Rapid point of care (POC) serological tests will then be used to confirm the clinical yaws diagnosis in the field, to allow for recruitment into the diagnostic evaluation study. Those with suspected yaws lesions will be tested with the SD Bioline syphilis test and those who test positive will be confirmed with the Chembio Dual Path Platform Syphilis Screen and Confirm POC test (herein DPP). As some cases of yaws occur in individuals who have not yet sero-converted, in order to improve the *Treponema pallidum pertenue* (TPE) prevalence estimate accuracy, we will collect lesion samples from all individuals with a dual seropositive DPP (treponemal and non-treponemal) and a subsample of the participants (1/10) negative for the SD Bioline or the DPP (either treponemal antibodies, non-treponemal antibodies or both). Two swabs, collected simultaneously from the same lesion, will be used for the diagnostic evaluation of the *T. pallidum* and *Haemophilus ducreyi* Loop-mediated isothermal amplification (TPHD LAMP) assay. Up to three further swabs may be collected from the same or additional lesions of the participant and from individuals with non-seroreactive tests but yaws-like lesions. We will also collect swabs of asymptomatic skin and of fomites of the house from some participants with and without yaws. These additional swabs will allow us to investigate other pathogenic causes of lesions using specific nucleic acid amplification tests and next generation sequencing. We will also be able to perform supplementary laboratory analysis on swab collection and DNA extraction methodologies, investigate the role fomites may have in the transmission of TPE and *H. ducreyi* and further understand the role of *H. ducreyi* as a cause of skin ulcers. No more than five lesion

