## 4 SUB-STUDY 1: MULTI-COUNTRY CASE SEARCHES AND EPIDEMIOLOGICAL ANALYSIS OF RISK FACTORS FOR YAWS

### 4.1 Objectives

- 1) Determine the prevalence of active and latent yaws in each setting using combined clinical, serological and molecular tools
- 2) Identify risk factors associated with active and latent yaws
- 3) Collect a representative dried blood spot sample library for future serological testing

We will undertake integrated case searches for individuals with yaws-like lesions. We will collect baseline clinical, demographic and risk factor information from participants. Individuals with clinical evidence of yaws will be tested with point-of-care serological tests (SD Bioline and Chembio DPP) in line with standard WHO recommendations, and will have lesion samples collected which will form the sample set required for sub-studies 2 & 3. We may record the presence of other skin conditions seen.

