### 4.3 Sample Size Considerations

We aim to screen approximately 60,000 individuals, 20,000 in each country. Of these we estimate 6000 individuals will present with yaws like lesions and 600 will have active yaws (i.e. present with yaw-like lesions and confirmed serologically). The remaining participants will be classed as either negative for yaws due to the absence of clinical signs or negative serology or suspected latent yaws if sero-reactive. We will aim to enrol all 6000 participants with yaws like lesions and a further 6000 without clinical yaws into this sub study. This will give us >80% power to detect risk factors associated with yaws with an odds ratio of 3. If resources allow, we will collect dried blood spots of half of the people enrolled into sub-study 1 giving us roughly 6000 dried blood spots samples. This would allow us to detect 5% seroprevalence with 0.5% precision, and a seroprevalence of 50% with a precision of 1.3%, which is deemed more than sufficient for a convenience sample .

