#### **4.5 Sample collection and storage**

As per WHO recommendations, people with clinically suspected yaws lesions will be screened using a *T. pallidum* POC test, and those that test positive will be confirmed with the DPP Screen and Confirm POC test detecting both treponemal and non-treponemal antibodies. In individuals with a positive DPP assay, we will collect lesion swabs for molecular testing according to WHO procedure  (Appendix C). As some cases of yaws occur in individuals who have not yet sero-converted we will also collect swabs from 1/10 people with suspected yaws but non-reactive serological tests. Two swab samples will be simultaneously obtained from each suspected yaws lesion (i.e. rolling both swabs over the lesion at the same time); one to conduct the TPHD-LAMP assay at the district level hospital, the other for PCR at the national reference laboratory for the detection of *T. pallidum* and *H. ducreyi* and monitoring resistance to antibiotics. A maximum of three other swabs may be taken, from the same or different lesions from people with or without yaws, and further swabs may be collected from asymptomatic skin or from fomites in the house, for additional infection detection analysis. Swab samples will be collected dry, or in suitable transport medium, and all tubes will be labelled with the participant's unique identification numbers and collection date. Half of those enrolled into sub-study 1 will be asked to provide a dried blood spot sample. This will give us an archive of around 6000 dried blood spots with which we can perform serological testing in the future. For this we will collect capillary finger blood onto a filter

paper designed specifically for blood collection following published procedures (see Appendix D). These will be air dried for at least 12 hours prior to being stored with desiccant sachets at ambient temperature.

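### No selection rule is stated for the 1/10 seronegative swabs, the 6,000 lesion-free participants or the blood-spot half, and no weighting is planned, so molecular prevalence and seroprevalence are open to bias

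*Combined protocol and SAP*

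**What the plan says.** Three subsets are drawn within sub-study 1 of the combined protocol and SAP.

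- **Lesion-free participants.** Section 4.4: "All people with lesions and around 6000 people without any clinical evidence will then be invited into sub study 1". The overview in 1.3 speaks of "A proportion of the yaws free participants", put at about 10%.
- **Seronegative lesion patients.** Section 1.3 plans swabs from "a subsample of the participants (1/10) negative for the SD Bioline or the DPP", and gives better accuracy of the *T. pallidum pertenue* (TPE) prevalence estimate as the reason. Section 4.5 repeats it: "we will also collect swabs from 1/10 people with suspected yaws but non-reactive serological tests". Sections 1.3 and 4.5 also allow up to three further swabs, including from seronegative people, with no stated fraction.
- **Blood spots.** Half of those enrolled, if resources allow (4.3, 4.5). The third objective in 4.1 is to "Collect a representative dried blood spot sample library for future serological testing". Section 4.3 gives a precision of 0.5 points at 5% seroprevalence and 1.3 points at 50%, which it says is "deemed more than sufficient for a convenience sample".

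Section 4.6 uses the blood spots to estimate latent cases in the community and seroprevalence at community and district level. Section 4.8 plans 95% confidence intervals for seroprevalence and describes no weighting. The only sample-selection method named is purposive selection, for quality-assurance samples in 5.6.

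**The concern.** All three subsets are meant to speak for people who were not sampled. At a fraction of 1/10, each seronegative positive stands for ten people, so whatever decides who is swabbed feeds directly into the molecular prevalence. The blood spots are to describe communities and districts, yet they come from a group deliberately loaded with lesion cases and are labelled both representative and a convenience sample. The lesion-free group also supplies some or all of the comparison subjects for the risk-factor models; 4.8 does not say which. If its members are chosen by availability, odds ratios for factors linked to availability are distorted.

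If no rule is set before enrolment, the sampling probabilities are unknown and later adjustment can only be partial.

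**Working it through.** **Inputs from the documents.** Section 4.3: "We aim to screen approximately 60,000 individuals, 20,000 in each country" and "Of these we estimate 6000 individuals will present with yaws like lesions and 600 will have active yaws". Hence:
- lesion cases not confirmed by serology: 6,000 − 600 = 5,400, of whom 1/10 = 540 are swabbed;
- lesion-free: 60,000 − 6,000 = 54,000, of whom 6,000 / 54,000 = 11.1% are enrolled;
- sub-study 1: 6,000 + 6,000 = 12,000, half of them lesion cases, against 6,000 / 60,000 = 10% of those screened;
- blood spots: about 6,000;
- qPCR positives among seropositives: 35% × 600 = 210 (5.3).

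**1. The plan's precision figure.** The simple-random-sample half-width is 1.96 × √(p(1−p)/n), with n = 6,000.
- p = 50%: 1.96 × √(0.25/6,000) = 1.27 points (stated: 1.3).
- p = 5%: 1.96 × √(0.0475/6,000) = 0.55 points (stated: 0.5, a match only if truncated).

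The pair is the simple-random-sample result, which presupposes a random, self-weighting sample.

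**2. Molecular TPE total under unequal selection.** Assumptions, not in the documents: a share p of the 5,400 seronegatives is truly positive, and positives are k times as likely to be swabbed as negatives. The positive share among those swabbed is p′ = kp / (kp + 1 − p). The true total is 210 + 5,400p and the scaled-up estimate is 210 + 5,400p′.

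| p | True total | Estimate, k = 2 | Error | Estimate, k = 0.5 | Error |
|---|---|---|---|---|---|
| 2% | 318 | 422 | +33% | 265 | −17% |
| 5% | 480 | 724 | +51% | 348 | −27% |
| 10% | 750 | 1,192 | +59% | 494 | −34% |

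Here k multiplies the probability of being swabbed. If instead the odds are doubled, with 10% swabbed overall, the totals are 403, 683 and 1,123, or +27%, +42% and +50%.

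With a random draw the scaled count is unbiased. Its 95% margin is 1.96 × 10 × √(540 p(1−p)) × √0.9: about ±60 cases at 2%, ±94 at 5% and ±130 at 10%. At k = 2 the errors are 422 − 318 = 104, 724 − 480 = 244 and 1,192 − 750 = 442 cases, all beyond those margins.

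**3. Unweighted seroprevalence.** Assumptions: blood spots split equally between lesion and lesion-free people; seroprevalence 10% to 20% in lesion cases and 5% in others.
- 10% in lesion cases: unweighted 0.5 × 10 + 0.5 × 5 = 7.5%; true 0.1 × 10 + 0.9 × 5 = 5.5%.
- 20% in lesion cases: unweighted 0.5 × 20 + 0.5 × 5 = 12.5%; true 0.1 × 20 + 0.9 × 5 = 6.5%.

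The errors of 2 and 6 points compare with a stated precision of 0.5. They arise even if both groups are drawn at random, so a random draw without weights is not enough.

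**4. Precision after weighting.** Relative weights are 0.1/0.5 = 0.2 for lesion cases and 0.9/0.5 = 1.8 for others. The Kish design effect is 2 × (0.2² + 1.8²) / (0.2 + 1.8)² = 1.64. Half-widths become 0.55 × √1.64 ≈ 0.71 points at 5% and 1.27 × √1.64 ≈ 1.62 points at 50%, before any allowance for village clustering.

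**The case against.** The strongest reply is that silence is not evidence of haphazard selection. A one-in-ten fraction fits a systematic every-tenth rule. Section 8.5 places sample procurement under SOPs, and neither those nor Appendices A to D are in the published text. This stands: a reader might infer that field staff will choose whom to swab, but the documents show only that no rule is stated.

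Second, 2.1.3 calls diagnosis from lesions alone unreliable, so staff may be poor at picking out true positives. That weakens the case for a factor as large as two and leaves the direction open. It does not remove the risk. Section 2.1.1 describes the papilloma as rich in bacteria, so a preference for one lesion type could shift positivity without anyone intending it.

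Third, demographic data, lesion type and photographs are recorded for enrolled lesion cases (4.4). Swabbed and unswabbed seronegatives can therefore be compared and standardised afterwards. That would be a partial repair, so the problem is not wholly beyond correction, but unrecorded reasons for selection would remain.

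Fourth, the blood spots depend on resources, and 1.9 lists the archive as a secondary objective. That lowers the stakes. Even so, 4.6 uses them to estimate latent yaws, whose prevalence is part of the first objective in 4.1.

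Three further readings go too far:
- **That all prevalence estimates are exposed.** Everyone screened is examined and all lesion cases receive the point-of-care serology, so prevalence by the 4.3 definition of active yaws involves no subsampling.
- **That every odds ratio is biased.** Only factors related to how lesion-free people are chosen are affected, and the 6,000 lesion cases are not subsampled.
- **That prevalence could be inflated ten-fold.** One extra positive adds ten people to a total of several hundred.

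**Conclusion.** The point holds as a gap in the stated design and analysis. The published text gives no selection rule for three subsets that must represent others. It describes the blood spots in two incompatible ways, quotes a precision that assumes simple random sampling, and describes no weighting for a set in which lesion cases are about five times over-represented (50% against 10%).

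Unequal selection could move the molecular TPE total by +33% to +59% or by −17% to −34%. These sizes rest on the assumed relative selection of 2 or 0.5 and assumed seronegative positivity of 2% to 10%; the documents support neither a value nor a direction. The seroprevalence error of 2 to 6 points rests on the assumed rates and equal split, but the imbalance behind it follows from the enrolment plan. If an SOP already holds a selection rule, what remains is to state it in the protocol, add the weights and reconcile 4.1 with 4.3. The change should be made before enrolment.

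**What to change.** - **4.4 and 4.5:** specify a random or systematic draw for the 1/10 swabs, the lesion-free group and the blood spots. The REDCap/ODK form can make it, or staff can take every k-th person within each community (for the lesion-free group, k is about 54,000 / 6,000 = 9). Record the achieved fraction in each community. Keep any additional seronegative swabs out of the prevalence estimate.
- **4.8:** use inverse sampling fractions for molecular prevalence and blood-spot seroprevalence, and name the comparison group for the odds ratios.
- **4.3:** remove the convenience-sample label so that it agrees with 4.1. Restate the precision as about 0.7 points at 5% and 1.6 points at 50%, for an equal lesion/lesion-free split weighted back to 10:90, and say that village clustering is not included.

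**Cost:** a tally of about 54,000 lesion-free people screened, slightly slower field work, and a less favourable stated precision. An every-k-th rule avoids opening a form for each lesion-free person. No extra participants or assays are needed.

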#### **4.5 Sample collection and storage**

As per WHO recommendations, people with clinically suspected yaws lesions will be screened using a *T. pallidum* POC test, and those that test positive will be confirmed with the DPP Screen and Confirm POC test detecting both treponemal and non-treponemal antibodies. In individuals with a positive DPP assay, we will collect lesion swabs for molecular testing according to WHO procedure  (Appendix C). As some cases of yaws occur in individuals who have not yet sero-converted we will also collect swabs from 1/10 people with suspected yaws but non-reactive serological tests. Two swab samples will be simultaneously obtained from each suspected yaws lesion (i.e. rolling both swabs over the lesion at the same time); one to conduct the TPHD-LAMP assay at the district level hospital, the other for PCR at the national reference laboratory for the detection of *T. pallidum* and *H. ducreyi* and monitoring resistance to antibiotics. A maximum of three other swabs may be taken, from the same or different lesions from people with or without yaws, and further swabs may be collected from asymptomatic skin or from fomites in the house, for additional infection detection analysis. Swab samples will be collected dry, or in suitable transport medium, and all tubes will be labelled with the participant's unique identification numbers and collection date. Half of those enrolled into sub-study 1 will be asked to provide a dried blood spot sample. This will give us an archive of around 6000 dried blood spots with which we can perform serological testing in the future. For this we will collect capillary finger blood onto a filter

paper designed specifically for blood collection following published procedures (see Appendix D). These will be air dried for at least 12 hours prior to being stored with desiccant sachets at ambient temperature.

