#### **3.1 Overall Study Outline and recruitment**

**Figure 1:** Flow chart of participant recruitment across all three-study countries. Initially we will screen 60,000 people of whom we expect 6000 will present with yaws-like lesions. These 6000 participants, along with 6000 without clinical evidence of yaws will be invited to take part in sub-study 1, the epidemiological analysis. All participants with clinically suspected yaws will be tested with a serology POC test, with positive results being confirmed by second POC test. Those with clinical and serological evidence of yaws will be invited to participate in sub-studies 2 and 3. Additionally, some participants from studies 1-3 along with healthcare workers and key stakeholders will be invited to enrol in study 4.

\* A DPP test is considered positive only if sero-reactive for both treponemal and non-treponemal antibodies.

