### 5.3 **Sample size**

We will collect samples for the TPHD LAMP evaluation from the 600 individuals with clinical and serological evidence of yaws, and an additional 10% of participants with clinical yaws but negative serology (sub-study 1). Based on the assumption that 35% of seropositive cases will also be positive by qPCR, this will result in approximately 210 qPCR positive *T. pallidum* cases and a similar number of *H. ducreyi* cases. This sample size will allow us to confirm that the TPHD-LAMP has both a sensitivity and specificity of at least 85% compared to the reference qPCR assays for both targets. This will also provide us with about 200 samples with unknown lesion aetiology to evaluate using next-generation sequencing as part of sub-Study 3.

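### Sections 1.3, 4.5 and 5.3 define the 1-in-10 paired-swab subsample differently, and 4.5 read literally leaves out lesion patients who are SD Bioline reactive but not DPP dual-positive

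*Combined protocol and SAP*

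**What the plan says.** Serology is stepwise. Lesion patients have a treponemal rapid test (SD Bioline), and only those who react go on to the DPP. Who then gives lesion swabs is described in several places.

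- Section 1.3: everyone with a dual-positive DPP, plus "a subsample of the participants (1/10) negative for the SD Bioline or the DPP (either treponemal antibodies, non-treponemal antibodies or both".
- Section 4.5, first group: "In individuals with a positive DPP assay, we will collect lesion swabs for molecular testing according to WHO procedure".
- Section 4.5, second group: "we will also collect swabs from 1/10 people with suspected yaws but non-reactive serological tests".
- Section 5.3: the dual-positives plus "an additional 10% of participants with clinical yaws but negative serology".
- Section 3.1, footnote to Figure 1: "A DPP test is considered positive only if sero-reactive for both treponemal and non-treponemal antibodies".

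Section 4.5 then describes the two swabs rolled together over the lesion, one for LAMP at district level and one for PCR at the reference laboratory. It also allows optional extra swabs: "A maximum of three other swabs may be taken, from the same or different lesions from people with or without yaws". Section 4.7 has unhealed lesions swabbed at week four.

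Section 4.3 classes the participants who are not active cases as negative or as "suspected latent yaws if sero-reactive".

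**The concern.** The 1-in-10 subsample is there because serology misses some cases. Section 1.3 says its purpose is a more accurate prevalence estimate for the yaws organism. Objective 1 of section 4.1 depends on it, because prevalence is to come from clinical, serological and molecular tools combined.

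Section 4.5 is where field staff would look for the sampling rule, and its wording is narrower than that of 1.3. The patients affected reacted on SD Bioline but then showed only one DPP line, or none. If a site leaves them out, their probability of entering the paired sample is zero. No later analysis can then estimate their qPCR positivity from study data, and the first-visit lesion cannot be sampled again. If some sites follow 1.3 and others 4.5, the subsample also means different things in different countries.

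**Working it through.** **Step 1. The plan's own figure.** Section 5.3 expects 35% of 600 seropositive cases to be qPCR positive: 600 x 0.35 = 210. This reproduces. It uses only the dual-positive group, so no reading of the subsample rule changes it.

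**Step 2. The rules side by side**, for a patient with a yaws-like lesion:

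| SD Bioline | DPP | 1.3 | 4.5, read literally |
|---|---|---|---|
| Negative | Not done | 1 in 10 | 1 in 10 |
| Reactive | Both lines | All | All |
| Reactive | One line only | 1 in 10 | Neither group |
| Reactive | No line | 1 in 10 | Neither group |

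In the last two rows the DPP is not positive under the 3.1 footnote, so the first group of 4.5 does not apply. The SD Bioline did react, so the patient's tests are not all non-reactive and the second group does not apply either. Section 5.3 does not settle the matter, because it does not say whether a mixed result counts as negative.

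**Step 3. Whether the other swabs fill the gap.** The extra swabs in 4.5 are optional and are meant for additional infection detection, not for the LAMP/PCR comparison. The week-four swab covers only lesions that have not healed after treatment was offered. Section 4.7 itself places all samples for the primary analysis at the first visit. Neither replaces the first-visit pair.

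**Step 4. Size.** Inputs from 4.3: 6,000 lesion patients, 600 of them serologically confirmed.

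- Not dual-positive: 6,000 - 600 = 5,400.
- Subsample under 1.3: 5,400 / 10 = 540. Total with paired swabs: 600 + 540 = 1,140.
- Subsample under a literal 4.5: 540 x (1 - d), where d is the share of the 5,400 who are SD Bioline reactive without a dual-positive DPP.

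The documents give no value for d. The values below are assumptions.

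| d | Patients in the group | Pairs under 1.3 | Subsample, literal 4.5 | Total with pairs |
|---|---|---|---|---|
| 5% | 270 | 27 | 513 | 1,113 |
| 10% | 540 | 54 | 486 | 1,086 |
| 20% | 1,080 | 108 | 432 | 1,032 |

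As a share of all lesion patients, the uncovered group would be 270 / 6,000 = 4.5% to 1,080 / 6,000 = 18%.

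**The case against.** The strongest reply is that 4.5 merely abbreviates 1.3. Both sections give the same reason for the subsample and the same fraction, and 1.3 itself uses a short form for seronegative patients soon after stating the full rule. Nothing in 4.5 expressly excludes discordant patients, and nothing gives 4.5 precedence over 1.3. Common training, SOPs and a pilot period (8.5) could bring the sites to one practice. All of this is fair, and it is why the point is an inconsistency to reconcile. A reader might infer that 4.5 flatly contradicts 1.3. The documents do not support that, because the shorthand reading is available.

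A reader might also infer that these patients can never be swabbed. That is not so: 1.3 gives them a route to the pair, 4.5 allows optional extra swabs, 4.7 provides a week-four swab, and 4.1 speaks generally of lesion samples from people with clinical yaws. What is missing is narrower: a stated route in 4.5 to the first-visit LAMP/PCR pair.

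Nor can the gap be turned into a count of missed infections to set against the 210. That would need a qPCR positivity for this group, which the documents do not give, and even under 1.3 only a tenth of the group would be swabbed.

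Finally, section 2.1.3 notes that treponemal antibodies are long-lived, so a reactive treponemal test with a negative non-treponemal line may reflect past infection. That weakens any claim that the group is rich in active cases. It does not justify leaving the group unsampled, because 1.3 chose to include it and only sampling can show its positivity.

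One argument favours the narrow reading. Section 4.5 justifies the subsample by people who have not yet seroconverted, and staff could reasonably decide that someone with a reactive SD Bioline is not such a person. The shorthand reading is therefore possible but not assured.

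**Conclusion.** The inconsistency is real and follows from the wording alone. Section 1.3 places SD Bioline reactive patients without a dual-positive DPP in the 1-in-10 subsample, 4.5 read literally names them in neither group, and 5.3 is silent on them. A site that follows 4.5 to the letter would omit this group from the molecular prevalence estimate and from the LAMP evaluation.

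The effect on numbers is modest and depends on an assumption: 27-108 fewer pairs out of 540 if the group is 5-20% of the 5,400. The expected 210 qPCR positives stand. The loss matters less for precision than for coverage, since one serological group would have no first-visit molecular data.

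The latent-yaws label in 4.3 is a smaller, related ambiguity. Point-of-care serology is given only to people with lesions, so the label could be read as covering discordant lesion patients, whereas 2.1.1 describes latent yaws as having no clinical signs. It can also be read as applying only to people without lesions, so a clarification is enough.

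**What to change.** - In 4.5 and 5.3, replace the description of the subsample with the 1.3 rule: 1 in 10 of all lesion patients who are not DPP dual-positive, that is, SD Bioline negative, or SD Bioline reactive with any DPP result other than both lines. Align the Figure 1 text in 3.1, which now mentions only those with clinical and serological evidence for sub-studies 2 and 3.
- Record the serological stratum for each lesion patient: SD Bioline negative, or SD Bioline reactive with treponemal line only, non-treponemal line only, or neither line. Results can then be reported by stratum.
- In 4.3, state that the latent-yaws label refers to sero-reactive people without lesions, in line with 2.1.1, and name lesion patients with discordant serology as their own analysis group.

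The cost is wording in the protocol and SOPs and one recorded variable. Compared with a literal 4.5, the added pairs are one tenth of the discordant group (27-108 at the assumed 5-20%). Compared with 1.3 there are none, since the 540 already include them. The change has to be in place before lesions are sampled, because a first-visit pair cannot be obtained later.
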